1.1.2 Nonclinical Studies

HighTide conducted an efficacy study of HTD1801 in rats subjected to BDL. HTD1801 at doses of 50 mg/kg and 150 mg/kg reduced ALP levels by 23.8% and 25.1% respectively, increased super oxide dismutase activity, and reduced malondialdehyde levels significantly, providing mechanistic evidence for the action of HTD1801 in the treatment of PSC. In addition, both doses ameliorated hepatocellular necrosis, reduced inflammation in the portal area, and inhibited bile duct proliferation, providing additional evidence of the potential for therapeutic effects of HTD1801 in PSC.

A second pharmacology study was conducted to evaluate the effects of HTD1801 on intestinal microbiota modification in a high-fat diet-induced hamster model of metabolic disorder. Recent clinical observations and animal findings have suggested an abundance of christensenellanceae^[25] and decreased parabacteroides^[26, 27] have a role in the etiopathogenesis of PSC.

The nonclinical toxicity profiles of both UDCA and BBR have been extensively studied. A full ICH M3 battery of nonclinical studies was performed with UDCA in support of NDA 20675. The toxicity profile of berberine was assessed in a battery on nonclinical studies conducted and/or reviewed by the National Toxicology program. These studies include single dose oral studies in mice and rats, in vitro and in vivo genotoxicity studies, as well as reproductive and developmental toxicity studies in mice and rats. [28-32] The pharmacokinetic and toxicity profile of HTD1801 has been evaluated in both rats and dogs. HighTide conducted toxicology studies of up to 2-weeks in rats (non-GLP) and up to 13-weeks in dogs (GLP). The results of these studies show that combined administration of UDCA and berberine as HTD1801 results in pharmacokinetic and toxicity profiles similar to that of the individual components UDCA and BBR. In addition, the 13-week GLP dog study provided data to qualify the toxicity profile of berberine in nonrodents and the safety of the combination of berberine and UDCA when administered as HTD1801.

Clinical Protocol

Formatt Dele

1.2 STUDY RATIONALE

This study is a dose ranging, proof-of-concept study with a PK substudy that follows the completion of a single ascending dose study in healthy volunteers.

1.3 DOSE RATIONALE

UDCA was FDA approved at a dose of 13-15 mg/kg/day, which is roughly 1,000 mg UDCA per day. BBR is widely used in dietary supplements in the United States at a recommended dose of 17 to 33 mg/kg/day, which is roughly 1 to 2 g/day. As shown in Table 2, the UDCA and BBR·Cl content of HTD1801 are comparable to that already shown to be safe clinically.

Table 2. Comparison of HTD1801 Clinical Dose with FDA Approved UDCA Dose and Recommended BBR Cl Dose

Compound	FDA Approved Clinical Dose (UDCA) / Dose used in dietary supplements (BBR- Cl)	HTD1801 Clinical Dose (33 mg/kg/day; 2000 mg/day) ^c
UDCA ^a	13-15 mg/kg/day (780-900 mg/day) ^b	18 mg/kg/day (1078 mg/day)
BBR Cla	17-33 mg/kg/day (1000-2000 mg/day)	17 mg/kg/day (1022 mg/day)

a: mg/kg doses calculated assuming a 60-kg adult

b: Safety at doses up to 25 mg/kg/day is supported by the published literature for PBC patients [33]

c: HTD1801 dose of 2000 mg/day is equivalent to 1022 mg/day BBR Cl and 1078 mg/day of UDCA.

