3.2.1 Inclusion Criteria

To be considered eligible to participate in this study, a subject must meet the inclusion criteria listed below:

- 1. Male or female between 18 and 75 years of age;
- 2. Have a clinical diagnosis of PSC as evident by chronic cholestasis of more than six months duration with either a consistent magnetic resonance cholangiopancreatography (MRCP) or endoscopic retrograde cholangiopancreatography (ERCP) showing sclerosing cholangitis;
- 3. If subjects have Inflammatory Bowel Disease (IBD) they will be eligible to participate. If a subject has IBD, documented evidence of IBD must have been evident by prior endoscopy or in previous medical records for ≥6 months. In addition, subjects may only enter the study with a Partial Mayo Score of 0-4, inclusively. Subjects who are on treatment are allowed, provided they are stable for 3 months if taking:
 - i. 5-amino salicylic acid drugs,
 - ii. azathioprine,
 - iii. 6-mercaptopurine, or methotrexate
 - iv. biologics;
- 4. Have a serum ALP $\geq 1.5 \times$ upper limit of normal (ULN);
- 5. Females of child-bearing potential and males participating in the study must either agree to use at least 2 approved barrier methods of contraception or be completely abstinent from sexual intercourse, if this is their usual and preferred lifestyle, throughout the duration of the study and for 3 months after stopping

- study drug. Females who are postmenopausal must have appropriate documentation;
- 6. Be able to understand and sign a written informed consent form (ICF);
- 7. Subjects receiving allowed concomitant medications need to be on stable therapy for 28 days prior to the Baseline visit, with the exception of UDCA, which should be stable for at least 6 weeks prior to the Baseline visit.

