4.5 CONCOMITANT MEDICATIONS

Any non-prohibited concomitant medications are to be continued during the study at the same dosage strength and frequency, and should not be taken within 1 hr prior to dosing or up to 6 hrs following dosing. Changes to concomitant medications are not to be made unless medically necessary. The need for the change must be documented, e.g., in response to an AE.

Patients should be cautioned about the use of glucose lowering drugs. The berberine component of HTD1801 is reported to lower blood glucose and may potentially cause hypoglycemia in patient taking other glucose lowering drugs at the same time. Patients who take glucose lowering drugs should be already aware of the most common symptoms of low blood sugar (dizziness, sweating, unusual hunger, shakiness, and a very rapid heartbeat) and should know how to react; in all these cases, however, patients should report these events to the Investigator.

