3.2. RANDOMIZATION AND BLINDING

Period 1: Placebo- and dose-controlled, parallel-group period

Subjects will be enrolled in equal numbers to one of the initial three treatment groups (placebo BID, HTD1801 500 mg BID, HTD1801 1000 mg BID) during the initial 6-week, double-blind, placebo- and dose-controlled, parallel-group period. Randomization will be centrally controlled, stratified

according to a co-existing diagnosis of IBD and UDCA status, and subjects will be assigned a pre-packaged and numbered treatment.

Subjects who were currently taking ursodeoxycholic acid (UDCA), or who had taken UDCA during the 6 weeks prior to randomization were to have completed a 6-week washout period before Baseline measurements per Protocol Version 1.2 dated 01 February 2018. The UDCA restriction was modified in Protocol Version 1.3 dated 12 June 2018 since only one subject had been enrolled in the earlier version of the protocol. Subjects on UDCA were eligible as long as the dose of UDCA was stable for at least 6 weeks prior to the Baseline visit.

Following the strategy session in the fall of 2018, an unblinded individual from the CRO, Cato Research, was tasked with determining whether the number of subjects taking UDCA was evenly distributed among the three study groups. This was found not to be so, with one dose cohort having no subjects who had previously been taking UDCA. While at the onset of the study, Period 1 randomization was stratified only by IBD diagnosis, this discovery spurred the inclusion of UDCA status as a stratification factor in an attempt to ensure even distribution between treatment groups for the primary analysis. UDCA status was therefore retroactively applied as a stratification factor to those 42 subjects who had already been randomized to Period 1, and gaps in these new strata were subsequently filled by 17 subjects enrolling from that point forward, with new randomization blocks prospectively added.

This new manual randomization process was initiated in November 2019. The autogenerated randomization process in the web-response system was too time consuming and costly to implement. This is managed by [name] (Boston Biostatistics Research Foundation, Inc.) in conjunction with an unblinded data base administrator, [name] (Cato Research Limited). The additional stratification factor of UDCA status will be included in the modeling.

Period 2: Dose-controlled extension

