3.3.2. Examination of Subject Subsets

Analysis of the primary endpoint will additionally be presented by IBD diagnosis as randomized and UDCA status when entering the study.

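### The protocol contradicts itself on whether background UDCA is taken with HTD1801, and the dose rationale's UDCA comparison covers the total dose only if it is stopped

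*Protocol*

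**What the plan says.** **Dose rationale (Protocol 1.3, Table 2).** Note c reads "HTD1801 dose of 2000 mg/day is equivalent to 1022 mg/day BBR Cl and 1078 mg/day of UDCA". Note a reads "mg/kg doses calculated assuming a 60-kg adult". The table gives 18 mg/kg/day of UDCA for the top dose, beside an approved 13-15 mg/kg/day (780-900 mg/day). Note b adds: "Safety at doses up to 25 mg/kg/day is supported by the published literature for PBC patients". The text above the table says "UDCA was FDA approved at a dose of 13-15 mg/kg/day, which is roughly 1,000 mg UDCA per day". Background UDCA is not mentioned.

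**Text that points to UDCA being continued.**
- Inclusion criterion 7 requires stable therapy for subjects on allowed concomitant medications, "with the exception of UDCA, which should be stable for at least 6 weeks prior to the Baseline visit". No upper dose is given. Section 5.1.1 carries the same stability rule.
- SAP 3.2 records that an earlier washout requirement was relaxed in protocol version 1.3: "Subjects on UDCA were eligible as long as the dose of UDCA was stable for at least 6 weeks prior to the Baseline visit".
- UDCA is not listed in Table 3 (prohibited medications).
- Section 4.5: "Any non-prohibited concomitant medications are to be continued during the study at the same dosage strength and frequency".

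**Text that points to UDCA being stopped.** Section 5.1.2 says that subjects who have been taking UDCA will be told to discontinue it before the Baseline visit.

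**Safety reporting.** UDCA status is a stratification factor (SAP 3.2), a model covariate (3.3.1) and a subgroup for efficacy: "Analysis of the primary endpoint will additionally be presented by IBD diagnosis as randomized and UDCA status when entering the study". GGT is split in the same way (5.2.5). Adverse event tables (5.3.1) and laboratory and vital-sign tables (5.3.2) are by treatment group only. The exposure table (5.1) counts milligrams of study drug only.

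**The concern.** HTD1801 delivers UDCA. A subject who keeps taking prescribed UDCA therefore receives two sources of it, and the dose rationale accounts for one. Whether this happens depends on which section a site follows, since Sections 4.5 and 5.1.2 give opposite instructions for the same drug.

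Two things are at stake. First, if sites follow Section 4.5, the total UDCA dose can pass the highest level for which Section 1.3 cites safety support, and the protocol nowhere computes that total. Second, safety and tolerability are secondary objectives, yet the planned safety tables would mix subjects with and without UDCA at entry. SAP 3.2 reports that UDCA users were unevenly spread over the arms, with one dose cohort having none when this was checked. A treatment comparison in the unsplit tables could therefore partly reflect UDCA status.

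**Working it through.** **Inputs**
- UDCA in HTD1801: 1078 mg/day at 1000 mg BID (Table 2, note c). At 500 mg BID half of this, 539 mg/day, assuming content proportional to dose.
- Body weight: 60 kg (Table 2, note a). Other weights are varied as an assumption.
- Reference level: 25 mg/kg/day (Table 2, note b).
- Background UDCA: not given for this population. Assumed at the protocol's own approved dose, either as 13-15 mg/kg/day, as fixed amounts of 780-900 mg/day, or as the rounded 1,000 mg/day in the text of Section 1.3.

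**Step 1: reproduce Table 2.** 1078 / 60 = 17.97 mg/kg/day (stated 18). 13 × 60 = 780 and 15 × 60 = 900 mg/day (as stated).

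**Step 2: UDCA stopped, as in Section 5.1.2.** The total is 17.97 mg/kg/day at 60 kg. It passes 25 only below 1078 / 25 = 43.1 kg.

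**Step 3: UDCA continued, as Section 4.5 reads.** Total = (UDCA from HTD1801) / weight + background in mg/kg/day. At 60 kg:

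| Background | 1000 mg BID | 500 mg BID |
|---|---|---|
| 13 mg/kg/day (780 mg/day) | 17.97 + 13 = 30.97 | 8.98 + 13 = 21.98 |
| 15 mg/kg/day (900 mg/day) | 17.97 + 15 = 32.97 | 8.98 + 15 = 23.98 |
| 1,000 mg/day | (1078 + 1000) / 60 = 34.63 | (539 + 1000) / 60 = 25.65 |

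Relative to 25, the 1000 mg BID totals are 24%, 32% and 39% higher.

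**Step 4: weight below which 1000 mg BID passes 25.**
- Background scaled to weight: 1078 / (25 − 13) = 89.8 kg; 1078 / (25 − 15) = 107.8 kg.
- Background as a fixed amount: (1078 + 780) / 25 = 74.3 kg; (1078 + 900) / 25 = 79.1 kg; (1078 + 1000) / 25 = 83.1 kg.

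The form of the assumption matters. At 80 kg, weight-scaled background gives 1078 / 80 + 13 = 26.5 to 1078 / 80 + 15 = 28.5. Fixed 780-900 mg/day gives 1858 / 80 = 23.2 to 1978 / 80 = 24.7, below the reference.

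**Step 5: who is affected.** The sum applies to anyone on 1000 mg BID who continues UDCA. That includes Period 1 placebo subjects re-randomised to 1000 mg BID in Period 2.

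**The case against.** The strongest reply is that Section 5.1.2 is the only UDCA-specific instruction for the dosing phase, while Section 4.5 is a general rule. The SAP also speaks of UDCA status on entering the study, which fits subjects who were stable and then stopped. On that reading the combined dose never arises. This stands as one coherent reading, and every figure in Step 3 is conditional on the other. It does not remove the conflict: criterion 7 places UDCA among allowed concomitant medications, Table 3 does not prohibit it, and Section 4.5 taken literally continues it.

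A reader might go further and infer three things that the documents do not support.
- *That the 1000 mg BID arm does exceed 25 mg/kg/day.* Entry on UDCA is not co-administration, and neither entry doses nor weights are given.
- *That the statement of comparability in Section 1.3 is false.* It concerns the UDCA contained in HTD1801, and for that it is arithmetically correct.
- *That no safety output could reveal UDCA use.* The concomitant-medication table and listing (SAP 5.3.3) could show it, the baseline table gives UDCA status by arm, and adverse events are listed by subject. The protocol also plans an exploratory exposure and adverse event analysis (8.2.6), though PK sampling covers only about 36 subjects and the SAP text supplied does not describe that analysis. There is also DSMB oversight and a liver-injury algorithm (6.9). None of these is described as giving total UDCA dose.

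It is also fair to say that safety subgroups in a trial this small will be thin. That limits what they can show, but not their use as description.

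**Conclusion.** The contradiction is real and has a consequence measurable against the protocol's own figure. With UDCA stopped, the top dose gives 18 mg/kg/day at 60 kg and the dose rationale stands. With UDCA continued at 13-15 mg/kg/day, it gives about 31-33 at 60 kg and passes 25 for subjects under about 90 kg (13 mg/kg) or 108 kg (15 mg/kg). With a fixed 780-900 mg/day it does so only under about 74-79 kg. At 500 mg BID the 60-kg total is 22-24, reaching 25.7 only with 1,000 mg/day.

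These figures rest on assumed background doses and weights. Because the 25 mg/kg/day figure comes from PBC literature and is not presented as a maximum, passing it means that the cited support would not cover the dose. It does not show harm. The reporting gap is a lesser point: the planned adverse event, laboratory, vital-sign and exposure tables show neither UDCA status nor total UDCA.

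**What to change.** 1. Reconcile Protocol 3.2.1 (criterion 7), 4.5, 4.6 (Table 3) and 5.1.1, and SAP 3.2, with Protocol 5.1.2, so that all state the same rule on background UDCA. Which rule applies is for the sponsor to decide. If the reconciled text allows co-administration, restate Section 1.3 and Table 2 on total UDCA (study drug plus background) for each arm.
2. In SAP 5.3.1 and 5.3.2, add descriptive summaries of treatment-emergent adverse events and liver chemistry by treatment and UDCA status at entry. If UDCA is co-administered and its dose is recorded, list total UDCA in mg/kg/day by subject.

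The cost is protocol wording and a few tables. Concomitant medications and weight are already in the schedule of events; whether the CRF captures concomitant-medication dose is not stated and should be checked. The drawback is small cells. SAP 3.2 implies 42 + 17 = 59 subjects over three arms and two UDCA strata, about 59 / 6 ≈ 10 per cell even if evenly spread, so the tables should be descriptive, without testing.

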2.0 OBJECTIVES

The primary objective of this proof-of-concept study is to evaluate the effects of HTD1801 on ALP in adult subjects with PSC.

The secondary objectives of this study are to evaluate the effects of HTD1801 on concurrent disease activity of inflammatory bowel disease (IBD), and on the safety and tolerability of HTD1801 over 18 weeks in adult subjects with PSC.

Pharmacokinetic (PK) and pharmacodynamics (PD) objectives include:

- Develop and validate population PK models for the components of HTD1801: berberine (BBR) and ursodeoxycholic acid (UDCA);
- Calculate individual single-dose and steady-state exposure metrics based on non-compartmental analysis methods in adult patients with PSC;
- Evaluate exposure-response models for efficacy;
- Evaluate the relationship between exposure, adverse events, and serious adverse events

3.0 STUDY DESIGN

3.1 BASIC DESIGN CHARACTERISTICS

This proof-of-concept study with a PK substudy will be conducted in three randomized, double-blind treatment periods in adult patients with PSC. The study design consists of an initial randomized, double-blind, placebo- and dose-controlled, parallel group period, followed by a dose-controlled extension period, followed by a placebo-controlled randomized withdrawal period.

- In the 1st period, subjects will be randomized to receive twice-daily doses of 500 mg, 1000 mg, or matching placebo for 6 weeks. The primary analysis will be based on this initial 6 week randomized, double-blind, placebo- and dose-controlled, parallel group period.
- Following the completion of that initial double-blinded, placebo- and dose-controlled parallel group period, subjects will be eligible to enroll in a 6-week extension period in which subjects previously randomized to 500 mg or 1,000 mg twice-daily (BID) will continue for 6 more weeks at that previous dose, while subjects previously randomized to placebo will be re-randomized to receive 6 weeks of either 500 mg or 1,000 mg BID. The study will remain double-blind.
- Following the completion of the 6-week experimental treatment extension, all subjects will be re-randomized to either continue on the active treatment they received in Period 2, or be assigned to placebo. The plan is for 50% of the subjects to remain on the experimental treatment at the previous dose and 50% will receive placebo.

3.2 STUDY POPULATION

Up to 90 patients with PSC will be enrolled as subjects. Eligibility will be established by the investigator on the basis of the inclusion and exclusion criteria. Approximately 36 subjects enrolled at selected sites will undergo additional blood draws for PK/PD analysis.

3.2.1 Inclusion Criteria

To be considered eligible to participate in this study, a subject must meet the inclusion criteria listed below:

- 1. Male or female between 18 and 75 years of age;
- 2. Have a clinical diagnosis of PSC as evident by chronic cholestasis of more than six months duration with either a consistent magnetic resonance cholangiopancreatography (MRCP) or endoscopic retrograde cholangiopancreatography (ERCP) showing sclerosing cholangitis;
- 3. If subjects have Inflammatory Bowel Disease (IBD) they will be eligible to participate. If a subject has IBD, documented evidence of IBD must have been evident by prior endoscopy or in previous medical records for ≥6 months. In addition, subjects may only enter the study with a Partial Mayo Score of 0-4, inclusively. Subjects who are on treatment are allowed, provided they are stable for 3 months if taking:
 - i. 5-amino salicylic acid drugs,
 - ii. azathioprine,
 - iii. 6-mercaptopurine, or methotrexate
 - iv. biologics;
- 4. Have a serum ALP $\geq 1.5 \times$ upper limit of normal (ULN);
- 5. Females of child-bearing potential and males participating in the study must either agree to use at least 2 approved barrier methods of contraception or be completely abstinent from sexual intercourse, if this is their usual and preferred lifestyle, throughout the duration of the study and for 3 months after stopping

- study drug. Females who are postmenopausal must have appropriate documentation;
- 6. Be able to understand and sign a written informed consent form (ICF);
- 7. Subjects receiving allowed concomitant medications need to be on stable therapy for 28 days prior to the Baseline visit, with the exception of UDCA, which should be stable for at least 6 weeks prior to the Baseline visit.

3.2.2 Exclusion Criteria

To be eligible for entry into the study, the subject must not meet any of the exclusion criteria listed below:

- Presence of documented secondary sclerosing cholangitis (such as ischemic cholangitis, recurrent pancreatitis, intraductal stone disease, severe bacterial cholangitis, surgical or blunt abdominal trauma, recurrent pyogenic cholangitis, choledocholithiasis, toxic sclerosing cholangitis due to chemical agents, or any other cause of secondary sclerosing cholangitis) on prior clinical investigations;
- 2. Small duct PSC;
- 3. Presence of percutaneous drain or bile duct stent;
- 4. History of cholangiocarcinoma or clinical suspicion of new dominant stricture within 1 year by MRCP/ERCP or clinical judgement. Presence of dominant stricture without ERCP evidence of cholangiocarcinoma is acceptable if stable for ≥ 1 year.;
- 5. Ascending cholangitis within 60 days prior to Screening;
- 6. Concomitant overlap syndrome with autoimmune hepatitis (AIH) as diagnosed by AST or ALT > 5x ULN, AND
 - i. positive smooth muscle antibody and/or liver-kidney microsomal antibody (LKM), or
 - ii. IgG >ULN, or
 - iii. Biopsy suggestive for AIH

- 7. Concomitant overlap syndrome with primary biliary cholangitis (PBC) as diagnosed by either:
 - i. positive AMA or
 - ii. biopsy suggestive for PBC
- 8. History of alcohol or substance abuse or dependence;
- 9. Prior or planned liver transplantation;
- 10. Presence of alternative causes of chronic liver disease, including alcoholic liver disease, nonalcoholic steatohepatitis, primary biliary cirrhosis, autoimmune hepatitis;
- 11. Platelet count below 125,000/mm³, albumin below 3.0 g/dL, International Normalized Ratio (INR) > 1.2, or a history of ascites, or encephalopathy, or history of esophageal variceal bleeding;
- 12. Anticoagulant therapy, with the exception of acetylsalicylic acid;
- 13. Severe active IBD or flare in colitis activity within the last 90 days requiring intensification of therapy beyond baseline treatment;
- 14. Use of oral prednisone/prednisolone > 10 mg/day;
- 15. Hospitalization for colitis within 90 days;
- 16. AST > 5 x ULN;
- 17. ALT > 5 x ULN;
- 18. Total bilirubin > 1.2 x ULN. If total bilirubin result at screening is > ULN but \leq 1.2 x ULN, a confirmatory total bilirubin should be collected after 21 days. If the confirmatory total bilirubin remains \leq 1.2 x ULN, and all other eligibility criteria continue to be met, the subject will be eligible.;
- 19. Evidence of Gilbert's Syndrome;
- 20. Immunoglobulin G4 (IgG4) > 2 × ULN at screening or evidence of IgG4-related sclerosing cholangitis;

- 21. Estimated glomerular filtration rate (eGFR) < 60mL/min/1.73m², calculated by the local laboratory;
- 22. Hemoglobin < 10 g/dL for males or females;
- 23. Hepatitis B surface antigen positive;
- 24. Hepatitis C antibody positive;
- 25. Human immunodeficiency virus (HIV)-1 or HIV-2 infection;
- 26. Glucose-6-phosphate dehydrogenase (G6PD) deficiency.
- 27. History of malignancy within the past 2 years or ongoing malignancy other than basal cell carcinoma, or resected noninvasive cutaneous squamous cell carcinoma;
- 28. Active, serious infections that require parenteral antibiotic or antifungal therapy within 30 days prior to Screening;
- 29. Major surgical procedure within 30 days of Screening or prior organ transplantation;
- 30. Females who are pregnant or breastfeeding;
- 31. Current or anticipated treatment with radiation therapy, cytotoxic chemotherapeutic agents and immune-modulating agents (such as systemic corticosteroids, interleukins, interferons);
- 32. Allergy to the clinical trial material or its components;
- 33. Received any experimental medications within 30 days prior to Screening;
- 34. Any other clinically significant disorders or prior therapy that, in the opinion of the investigator, would make the subject unsuitable for the study or unable to comply with the dosing and protocol requirements.

